6.11.3.2 Tipping Point Analysis

If the primary efficacy analysis in Section 6.11.2 significantly favors any NYX-2925 treatment group, a tipping point sensitivity analysis⁴ for the primary efficacy endpoint will be conducted to investigate how severe the departure from the MAR assumption data must be to overturn conclusion from the primary analysis.

In this analysis, the assumption will be that that missing data in the NYX-2925 groups follows a MNAR pattern. A tipping point-based approach will be used such that the trajectories of the subjects in the NYX-2925 groups after early withdrawal are assumed to be worse than placebo by a fixed amount (δ). The value of δ is the adjustment added during imputation to the change from baseline NRS scores at each visit after study discontinuation. This increment is added only to the imputed change from baseline NRS scores at visits after study discontinuation of the subjects in NYX-2925. The value of δ will increase in increments of 0.5 (i.e., 1.0, 1.5, 2.0) up to the point at which the treatment difference at Week 12 is no longer statistically significant. This analysis provides a measure of the degree by which the subjects in the NYX-2925 groups who discontinued early would need to be worse (compared to those who did not discontinue) at each post-discontinuation visit in order for the null hypothesis of no treatment difference to no longer be rejected. Intercurrent events will be imputed by BLOCF as estimand in Section 6.11.1.1. Each imputed dataset produced through PROC MI procedure will be processed as follows:

- All values imputed for the placebo group will remain unchanged
- All values imputed for the NYX-2925 groups will be incremented by a value of δ , which will vary from 0 up to a value by which statistical significance is not reached
- The modified data will be analyzed using similar analysis as described in Section 6.11.2.

Results will then be combined using PROC MIANALYZE and will consequently be recorded

The “tipping point” is defined as the value of δ at which the result changes from a statistically significant treatment effect to a treatment effect that is no longer statistically significant. The larger the value of δ , the more robust the conclusion from the primary analysis with respect to assumptions around missing data.

6.11.3.3 Supportive Analysis

6.11.3.3.1 Analysis of Covariance on change from baseline to Week 12 in the weekly mean of the NRS score assessing average pain intensity in the past 24 hours

To assess the robustness of the result observed for the primary endpoint, the one-sided Analysis of Covariance (ANCOVA) model with site and treatment as factors, and baseline NRS score as a covariate will be employed as a supportive analysis.

The following is the sample SAS code that will be used to implement this analysis:

```
PROC MIXED DATA= DATAIN;
  CLASS TREATMENT SITE;
  MODEL CFB WEEK12 = TREATMENT SITE BASELINE / SOLUTION;
  * extract two-sided 95%CI of LS MEANS each treatment groups by week;
  LSMEANS TREATMENT / CL DIFF;
  * extract one-sided 95%CI of LS MEANS each treatment groups by week;
  LSMEANS TREATMENT / CL DIFF ALPHA=0.10;
  RUN;
```

The LS means, SEs, and 95% CIs will be provided for each treatment group at all weeks alongside treatment difference estimates, SE, and one-sided CIs and p-values

6.11.3.3.2 Pooled Analysis

To provide supportive evidence for the primary objective, a pooled analysis will be performed where the NYX-2925 50 mg group will be pooled with the NYX-2925 100 mg group and compared against the placebo group. The REML-based MMRM model in Section 6.11.2 will be repeated with site, treatment group (NYX-2925-treated group versus Placebo-treated group), week, baseline NRS score, and treatment-by-week interaction as terms in the model. A line plot showing the LS means and 95% CIs of the weekly mean NRS scores from Week 1 through Week 12 for pooled treatment group and placebo group will be presented.

6.11.3.4 [REDACTED]

6.11.4 Secondary Endpoints

All secondary endpoints will be analyzed by one-sided testing using the mITT population. The two-sided testing will be also performed for all secondary endpoints, unless otherwise stated.

6.11.4.1 Percentage of Subjects “much improved” or “very much improved” on the Patient Global Impression of Change (PGI-C) at Week 12

Analysis will utilize the one-sided Chi-square test to compare the risk between treatment groups, using the following SAS code:

```
PROC FREQ DATA= DATAIN ORDER=DATA;
TABLES TREATMENT*RESP / riskdiff (column=2 method=wald equal var=null)
ALPHA=0.10;
ODS OUTPUT PDIFFCLS = DIFF1 PDIFFTEST = PVAL1;
RUN;
```

The number and percentage of subjects ‘much improved’ or ‘very much improved’ by treatment at each visit will be presented. The risk difference for NYX-2925 50 mg vs placebo and NYX-2925 100 mg vs placebo, the corresponding 1-sided 95% CI and 1-sided p-value for the Chi Square statistic will also be provided by visit. The lower limit of the 95% one-sided CI for the risk difference will be extracted as the lower limit of the 90% two-sided CI using the ALPHA=0.10 option with the upper limit being set to positive infinity. 2-sided Chi Square test will be performed as well with the risk difference, corresponding 2-sided 95% CI and 2-sided p-value.

Summary statistics for the PGI-C as a continuous score will also be provided by treatment group at each visit. Scores will be analyzed using the same REML-based MMRM as in the primary analysis, except with the exclusion of a baseline covariate.

The analysis will be repeated for Week 4 and Week 8. Observed scores will also be presented by treatment group. The LS means, corresponding SEs, and 95% CIs for each treatment group will be presented at each week along with the LS mean difference, corresponding SE, 1-sided 95% CI and 1-sided p-value.

A listing of all PGI-C scores will also be provided.

The analysis will be repeated for Weeks 4, 8, and 12 and observed value of PGI-C, and number and percentage of subjects ‘much improved’ or ‘very much improved’ on PGI-C will be presented.

6.11.4.2 Change from baseline in the weekly mean of the Daily Sleep Interference Scale (DSIS) scores at Week 12

A similar approach in modeling the REML-based MMRM as in the primary analysis will be applied to the change from baseline in the weekly mean of the DSIS scores at Week 12 except that the outcome variable will be change from baseline in the weekly mean of the DSIS scores at Weeks 1 through 12, and the fixed effects are as follows: site, treatment group, week, baseline DSIS score, and treatment-by-week interaction as terms in the model. Observed DSIS scores at baseline and at each week, as well as the change from baseline DSIS scores at each week will be presented by treatment group. The LS means, corresponding SEs, and 95% CIs for each treatment group will also be presented at each week. Additionally, the estimate, corresponding SE, one-sided 95% CI, and one-sided p-value of the treatment difference at Week 12 will be presented. The two-sided testing will also be performed.

6.11.4.3 Percentage of subjects achieving $\geq 30\%$ and $\geq 50\%$ reduction from baseline in the weekly mean NRS average pain intensity related to fibromyalgia at Week 12

The number and percentage of subjects achieving $\geq 30\%$ and $\geq 50\%$ reduction from baseline in the weekly mean NRS will be analyzed using the Cochran-Mantel-Haenszel method and presented as described in Section 6.11.4.1.

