Beginning at Week-1, fibromyalgia related pain intensity and rescue medication use will be recorded in the study-issued handheld device daily at bedtime. Subjects will enter their average pain intensity and total rescue medication use during the past 24 hours. Pain intensity will be recorded using an 11-point NRS, with 0 being no pain and 10 being the worst possible pain. Every morning upon awakening, subjects will complete the Daily Sleep Interference Scale (DSIS) via their study-issued handheld device.

The following scales will be completed at the Screening Visit (Visit 1): PGI-S, 2016 ACR Fibromyalgia Criteria, [REDACTED] MINI, and the S-STS.

Screening Period: Week -1(as needed)

Subjects taking no concomitant analgesic medication for their fibromyalgia at Visit 1 may directly begin Week -1 of the Screening Period.

Baseline Visit: Week 0/Visit 2

At Visit 2 (Baseline Visit), study personnel will verify eligibility with the inclusion and exclusion criteria while the subjects are on site and perform safety assessments.

The appropriate use of rescue medication will be assessed by inventory of the returned tablets, as well as by subject interview. Use of concomitant medications will be documented. Additional procedures during Visit 1 will include the S-STS, an electrocardiogram and vital signs (blood pressure and pulse after sitting or lying supine for at least five minutes). Blood (8 hour fast) and urine samples will be collected for hematology, chemistry, and urinalysis testing. Subjects will undergo a drug screen using a local urine testing kit. Subjects who test positive for benzodiazepines inconsistent with protocol specified allowed prescriptions, psychoactive cannabinoids (e.g., marijuana, THC) inconsistent with subject reported use, opioids, PCP, cocaine, or amphetamines will not be allowed to continue in the study. Female subjects of childbearing potential will be tested for pregnancy using a local urine testing kit and will be counseled to continue using highly effective contraception.

Pain scores reported by subjects during the Screening Period will be evaluated by the interactive response technology (IRT) system for raw score and for variability among scores after transmission of

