Subjects will be instructed to continue entering their average pain intensity and rescue medication use over the past 24 hours into their study issued handheld device every night. Every morning upon awakening, subjects will complete the DSIS and confirm they have taken their study medication for the day via their study-issued handheld device. Diary compliance will be reviewed at each study visit by the study staff, and reporting instructions will be reinforced. Subjects will be reminded on appropriate expectations around their participation in a clinical study and the importance of consistently and accurately reporting their pain intensity throughout the study. Review of the APR® and PRR® materials will be repeated for all subjects as refresher training or based on findings of an ongoing blinded data review (e.g., if pain score variability is increased on a subject or site level) via the aLearn® portal.

The following scales will be completed at the Baseline Visit (Visit 2): the Fibromyalgia Impact Questionnaire - Revised (FIQR), [REDACTED] the Patient Reported Outcomes Measurement Information System – Fibromyalgia (PROMIS_{FM}) [Sleep Disturbance Short Form, Fatigue Profile Short Form, Physical Function Short Form], PGI-S and S-STS.

The subject will be given a printed copy of the study specific S-STS to take home and complete during the Week 2/Visit 3 telephone or videoconference visit.

Treatment Period: Week 2/Visit 3

Subjects will be contacted by the clinic via telephone or videoconference at the end of Week 2 (Visit 3) for assessment of compliance with study drug, use of rescue medication and diary entries. The appropriate use of study drug and rescue medication will be assessed by subject interview. Subjects will be reminded to take one capsule of study drug by mouth once daily. The subject will be reminded not to exceed 3 g/day (one to two 500 mg tablets every 6 hours as needed) of rescue medication for pain related to fibromyalgia.

Diary compliance will be reviewed by the study staff and reporting instructions will be reinforced. Adverse events will be assessed by asking the subjects a nonleading question. Misuse and abuse-related events will be assessed using the Misuse, Abuse, and Diversion Drug Event Reporting System® (MADDERS [Analgesic Solutions, Wayland, MA]). Use of concomitant medications will be documented.

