6.11.2 Primary Efficacy Analysis

A one-tailed restricted maximum likelihood (REML)-based mixed model for repeated measures (MMRM) with one sided 95% CI will be utilized to assess the difference between treatment groups with respect to change from baseline to Week 12 in the weekly mean of the NRS score assessing average pain intensity in the past 24 hours.

The MMRM model will have site, treatment group, week, baseline NRS score, and treatment-by-week interaction as terms in the model. The unstructured covariance (UN) will be utilized as the within-subject covariance structure. In the event that the model fails to converge using the UN, the

Fisher scoring algorithm (via the SCORING option of the PROC MIXED statement) will be used to obtain the initial values of covariance parameters, otherwise, no-diagonal factor analytic structure (via the TYPE = FA0(T) option of the REPEATED statement) will be used as another option. When the above strategy fails, the successive univariate regression method will be applied. The Kenward-Roger degrees of freedom correction will also be used for this analysis.

The estimate of the difference between NYX-2925 50 mg versus placebo and NYX-2925 100 mg versus placebo at Week 12 and standard error (SE) will be derived from this model. Observed NRS scores at baseline and at each week, as well as their change from baseline at each week will be presented by treatment groups. The LS means, corresponding SEs, and 95% CI for each treatment group, the treatment difference of LS means, corresponding SEs, 1-sided 95% CI and 1-sided p-value at each week will be presented. The upper limit of the 95% CI of treatment difference will be extracted using ALPHA=0.10 statement for the bound in the unfavorable direction, and the limit in the favorable direction will be set to negative infinity.

The following is the sample SAS code that will be used for this analysis:

```
PROC MIXED DATA= DATAIN;
  CLASS USUBJID TREATMENT WEEK SITE;
  MODEL CHG = TREATMENT WEEK SITE TREATMENT*WEEK BASELINE / DDFM=KR;
  REPEATED WEEK / SUBJECT=USUBJID TYPE=UN;
  * extract two-sided 95%CI of LS MEANS each treatment groups by week;
  LSMEANS TREATMENT*WEEK / DIFF CL;
  * extract one-sided 95%CI of LS MEANS each treatment groups by week;
  LSMEANS TREATMENT*WEEK / DIFF CL ALPHA=0.10;
  RUN;
```

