A similar approach in modeling the REML-based MMRM as in the primary analysis will be applied to the weekly dosage of acetaminophen used except that the outcome variable will be the dosage of acetaminophen used at Weeks 1 through 12, and the fixed effects are as follows: study site, treatment group, week, and treatment-by-week interaction as terms in the model. The LS means, corresponding SEs, and 95% CIs for each treatment group will also be presented at each week. Additionally, estimate, corresponding SE, and p-value of the treatment difference at each week will also be presented.

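### The rescue-dose MMRM leaves out baseline acetaminophen use, which the diary already records, and so gives up precision without causing bias

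*SAP*

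**What the plan says.** **Rescue dose.** SAP 6.11.4.9 models the weekly dosage of acetaminophen at Weeks 1 through 12. The outcome is the dose itself, not a change score, and the fixed effects are "study site, treatment group, week, and treatment-by-week interaction as terms in the model". Treatment differences with p-values are to be shown at each week.

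**The other MMRMs.** For the primary model, SAP 6.11.2 states: "The MMRM model will have site, treatment group, week, baseline NRS score, and treatment-by-week interaction as terms in the model". The DSIS model has "site, treatment group, week, baseline DSIS score, and treatment-by-week interaction as terms in the model". The FIQR and PROMIS models (6.11.4.4 to 6.11.4.7) likewise include the baseline of the score being analysed.

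**What is collected.** The Protocol Synopsis says: "Beginning at Week-1, fibromyalgia related pain intensity and rescue medication use will be recorded in the study-issued handheld device daily at bedtime". SAP 6.2.2 defines baseline for weekly-mean endpoints over study days -7 to -1. SAP 6.2.19, which derives the rescue variables, defines no baseline dose.

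**PGI-C.** SAP 6.11.4.1 fits the continuous score with the primary model, "except with the exclusion of a baseline covariate". Protocol 9.2.9 describes PGI-C as a rating of change since the study began. Baseline NRS and PGI-S are both available before dosing.

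**The concern.** Amount of rescue medication used is part of a named secondary endpoint. The Protocol Synopsis planned only a descriptive summary; the SAP adds modelled treatment differences and p-values, so the quality of the model now matters. Because the outcome is raw dose, a subject's habitual use enters the model nowhere. Any part of the on-treatment spread that the baseline week could predict stays in the residual variance and widens the confidence interval.

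Rescue dose is also the one MMRM outcome described in the readable text that has its own recorded baseline and is not adjusted for it. At stake is the precision of that comparison. Its validity is not in question.

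**Working it through.** **1. The plan's own figure.** SAP section 4 gives about 88% power for the primary endpoint with 85 per arm, difference 0.73, SD 1.7 and one-sided alpha 0.05.
- Standard error = 1.7 × sqrt(2/85) = 0.2608; 0.73/0.2608 = 2.799.
- One-sided: Φ(2.799 − 1.645) = 0.876, which reproduces the 88%.
- Two-sided: Φ(2.799 − 1.960) = 0.799, which matches the 80% in Protocol 12.1.

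Neither figure concerns the rescue-dose or PGI-C model; the documents state no precision for those.

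**2. Formula.** With treatment, week and their interaction in the model and an unstructured covariance, the complete-data treatment contrast at a given week is in essence the difference in means at that week. Adding one baseline covariate changes its standard error by

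f = SE(adjusted)/SE(unadjusted) = sqrt[(1 − ρ²) × df/(df − 1)]

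where ρ is the within-arm correlation of the covariate with the outcome. Inputs: N = 3 × 85 = 255 and df = 255 − 3 = 252. **ρ is an assumption throughout.**

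**3. Results.** The last column is the power after adjustment of a comparison that has 80% one-sided power without it: Φ[(1.645 + 0.842)/f − 1.645].

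| ρ | f | SE reduction | Equivalent share of sample, 1 − f² | Power |
|---|---|---|---|---|
| 0.1 | 0.997 | 0.3% | 0.6% | 80.2% |
| 0.2 | 0.982 | 1.8% | 3.6% | 81.3% |
| 0.3 | 0.956 | 4.4% | 8.6% | 83.1% |
| 0.4 | 0.918 | 8.2% | 15.7% | 85.6% |
| 0.5 | 0.868 | 13.2% | 24.7% | 88.9% |
| 0.6 | 0.802 | 19.8% | 35.7% | 92.7% |
| 0.7 | 0.716 | 28.4% | 48.8% | 96.6% |

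A two-arm simulation with 85 per arm gave f of 0.996, 0.981, 0.963, 0.873 and 0.713 at ρ of 0.1, 0.2, 0.3, 0.5 and 0.7, in line with the formula.

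**4. Break-even.** f = 1 when ρ² = 1/df, so ρ = sqrt(1/252) = 0.063. Allowing for the most sites the protocol permits, 52, df = 255 − 3 − 51 = 201 and break-even is sqrt(1/201) = 0.071. Adjustment is very unlikely to cost anything.

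**5. Rescue dose.** The covariate is the same quantity, from the same diary, one week before dosing. At ρ of 0.4 to 0.7 the standard error falls by 8.2% to 28.4%.

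**6. PGI-C.** The covariate would be a different measure, so a lower range is assumed. At ρ of 0.1 to 0.3 with baseline NRS, the reduction is 0.3% to 4.4%. PGI-S would give less: it has four levels and Visit 1 entry requires moderate or severe. With the covariate cut to two levels, the simulated reduction was about 0%, 1% and 3% at underlying ρ of 0.1, 0.2 and 0.3.

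**The case against.** The strongest reply is that this is a preference about efficiency in one component of one secondary endpoint. The rescue MMRM already goes beyond the descriptive summary in the Protocol Synopsis, SAP 6.11.6 applies no multiplicity control to secondary endpoints, and every correlation used here is assumed. That stands as a limit on the point's weight. It does not explain why rescue dose departs from the pattern of the other models.

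The PGI-C omission is defensible. A rating of change has no pre-treatment value, so dropping the baseline term follows from the scale. The continuous model also only supplements the Week 12 responder percentage, which is tested by chi-square. A reader might infer that precision is lost there on a similar scale; the arithmetic does not show it.

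Three further inferences go beyond the documents:
- **Bias.** A reader might infer that chance imbalance in baseline use biases the treatment difference. Under randomisation the unadjusted comparison is unbiased, its standard error already allows for such imbalance, and type I error is not inflated.
- **Variance.** A reader might infer that differences between people dominate the variance of rescue dose. That is plausible, but no variance component is given.
- **Role.** A reader might infer that rescue use is the main support for the pain result. The SAP gives the supportive role to the ANCOVA and the pooled-dose analysis.

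The objection is also right that the covariate needs a rule for missing diary days, and that a covariate-by-week term would go beyond the SAP's own models.

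**Conclusion.** The point holds for rescue dose. The model omits a recorded baseline of its own outcome, against the SAP's practice elsewhere, and loses precision as a result. The loss is a standard error that adjustment would make about 8% to 28% smaller if ρ is 0.4 to 0.7, and any ρ above about 0.06 gives some gain. This rests on an assumed correlation, a roughly linear relation between baseline and on-treatment dose, and 85 subjects per arm.

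For PGI-C there is only an optional refinement worth about 0% to 4% of the standard error. The primary analysis, the PGI-C responder test and the test of the proportion using rescue medication are all unaffected.

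**What to change.** - **SAP 6.2.19:** derive a baseline acetaminophen dose over Days -7 to -1. One workable rule is mean daily dose over available diary days × 7, so that a missing day is not counted as zero use. State the minimum number of diary days and what happens below it; the five-of-seven minimum in 6.2.17.1 is written for baseline NRS only.
- **SAP 6.11.4.9:** add this baseline dose as a covariate. A covariate-by-week interaction is optional.
- **SAP 6.11.4.1:** optionally add baseline mean NRS to the continuous PGI-C model. NRS is preferable to PGI-S because the range of PGI-S is restricted at entry.

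The cost is a few lines of SAP text and one derived variable, with no new data. Timing matters: the SAP addendum states that it was written after database lock and unblinding, and the changes it details do not include this model. If the adjustment is made after unblinding, keep the planned model as the reported analysis and show the adjusted one beside it, labelled post hoc and supplementary.

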6.11.4.4 Change from Baseline in the Fibromyalgia Impact Questionnaire – Revised (FIQR) score

A similar approach in modeling the REML-based MMRM as in the primary analysis will be applied to the change from baseline in the Fibromyalgia Impact Questionnaire-Revised (FIQR) total score at Week 12 except that the outcome variable will be change from baseline in the weekly mean of the FIQR total scores at Weeks 1 through 12, and the fixed effects are as follows: site, treatment group, week, baseline FIQR total score, and treatment-by-week interaction as terms in the model. Observed FIQR total scores and subscores at baseline, Week 4, Week 8 and Week 12, as well as the change from baseline FIQR total scores and subscores at each visit will be presented by treatment group. The LS means, corresponding SEs, and 95% CIs for each treatment group will also be presented. Additionally, the estimate, corresponding SE, one-sided 95% CI, and one-sided p-value of the treatment difference at Week 12 will be presented. The two-sided testing will also be performed.

6.11.4.5 Change from Baseline in the Patient Reported Outcomes Measurement Information System (PROMIS) sleep disturbance score

A similar approach in modeling the REML-based MMRM as in the primary analysis will be applied to the change from baseline in the PROMIS sleep disturbance score at Week 4, Week 8, and Week 12 except that the outcome variable will be change from baseline in the weekly mean of the PROMIS sleep disturbance score, and the fixed effects are as follows: site, treatment group, week, baseline PROMIS sleep disturbance T-score, and treatment-by-week interaction as terms in the model. Observed PROMIS sleep disturbance score at baseline, Week 4, Week 8, and Week 12, as well as the change from baseline will be presented by treatment groups. The LS means, corresponding SEs, and 95% CIs for each treatment group will also be presented at each week. Additionally, the estimate, corresponding SE, one -sided 95% CI, and one -sided p-value of the treatment difference at Week 12 will be presented. The two-sided testing will also be performed.

6.11.4.6 Change from Baseline to Week 12 in the Patient Reported Outcomes Measurement Information System – Fibromyalgia (PROMIS_{FM}) fatigue profile score

A similar approach in modeling the REML-based MMRM as in the primary analysis will be applied to the change from baseline in each PROMIS_{FM} fatigue profile subscore at Week 4, Week 8, and Week 12 except that the outcome variable will be change from baseline in the weekly mean of the PROMIS_{FM} fatigue profile subscore, and the fixed effects are as follows: site, treatment

group, week, baseline PROMIS_{FM} fatigue profile subscore, and treatment-by-week interaction as terms in the model. Observed PROMIS_{FM} fatigue profile subscore at baseline, Week 4, Week 8, and Week 12, as well as the change from baseline will be presented by treatment group. The LS means, corresponding SEs, and 95% CIs for each treatment group will also be presented at each week. Additionally, the estimate, corresponding SE, one-sided 95% CI, and one-sided p-value of the treatment difference at Week 12 will be presented. The two-sided testing will also be performed.

6.11.4.7 Change from Baseline to Week 12 in the Patient Reported Outcomes Measurement Information System (PROMIS) physical function score

A similar approach in modeling the REML-based MMRM as in the primary analysis will be applied to the change from baseline in the PROMIS physical function T-score at Week 4, Week 8, and Week 12 except that the outcome variable will be change from baseline in the weekly mean of the PROMIS physical function score, and the fixed effects are as follows: site, treatment group, week, baseline PROMIS physical function score, and treatment-by-week interaction as terms in the model. Observed PROMIS fatigue profile score at baseline, Week 4, Week 8, and Week 12, as well as the change from baseline will be presented by treatment group. The LS means, corresponding SEs, and 95% CIs for each treatment group will also be presented at each week. Additionally, the estimate, corresponding SE, one-sided 95% CI, and one-sided p-value of the treatment difference at Week 12 will be presented. The two-sided testing will also be performed.

6.11.4.8 Cumulative response (percent reduction from baseline) in the weekly mean NRS average pain intensity at Week 12

A cumulative responder analysis will be conducted for the primary efficacy endpoint. in this analysis, response is defined as the percent reduction from baseline in the weekly mean NRS average pain intensity at Week 12. Subjects who prematurely discontinue from treatment prior to Week 12 will be defined as a non-responder (i.e., 0% reduction/improvement in percent reduction from baseline). Patients with a worsening in the weekly mean NRS score will be categorized as having a 0% improvement. A cumulative response curve will be generated in which the response level is on the x-axis (-50% to 100%, in 10% intervals, with reference lines at 30% and 50%) while the associated cumulative proportion of subjects calculated for that response level (i.e., percent reduction from baseline) is on the y-axis. The difference in the cumulative response curves between treatment groups will be analyzed using a Kolmogorov-Smirnov test. This test determines

if two samples of data are from the same distribution. The D statistic and 1-sided p-value will be provided. The Kolmogorov-Smirnov test will be performed using the D option in PROC NPAR1WAY in SAS:

```
PROC NPAR1WAY DATA= DATAIN D;  
CLASS TREATMENT;  
VAR RESP;  
EXACT KS;  
RUN;
```

6.11.4.9 Use of rescue medication, including the proportion of subjects using rescue medication, the frequency and amount used

The total number of tablets taken and percentage of rescue-free days per week will be summarized by treatment group. The proportion of subjects that used rescue medication (one or more tablets) at any point after the first dose of study drug will also be summarized by treatment group. A one-sided Chi-square test on equality of two proportions will be performed to compare the treatment groups. The difference in proportion with 95% CI of 1-sided testing will be provided. The SAS code will be as following:

```
PROC FREQ DATA=DATAIN;  
TABLES TRT01PN*RMUSE/ RISKDIFF (EQUAL VAR=NULL CL=WALD) ALPHA=0.10;  
ODS OUTPUT PDIFFCLS = DIFF1 PDIFFTEST = PVAL1;  
RUN;
```

A similar approach in modeling the REML-based MMRM as in the primary analysis will be applied to the weekly dosage of acetaminophen used except that the outcome variable will be the dosage of acetaminophen used at Weeks 1 through 12, and the fixed effects are as follows: study site, treatment group, week, and treatment-by-week interaction as terms in the model. The LS means, corresponding SEs, and 95% CIs for each treatment group will also be presented at each week. Additionally, estimate, corresponding SE, and p-value of the treatment difference at each week will also be presented.

